non-invasive blood pressure (BP), and oxygen saturation (SpO₂) will be checked in the holding room. We will also record all medications taken on the day of surgery. Once in the operating room and following placement of vital sign monitors, another non-invasive BP will be checked prior to anesthetic induction. This reading will be used as the baseline systolic blood pressure (SBP). Sequential Compression Devices (SCD) will be used for venous thromboembolism (VTE) prophylaxis during surgery and these will be applied prior to induction of general anesthesia. General anesthesia will then be induced with 1.5 mg/kg of propofol followed by 0.8 mg/kg rocuronium and the patient will be intubated. If the dose of propofol is inadequate to achieve loss of consciousness, additional propofol may be given at the discretion of the attending anesthesiologist. In addition, a rapid sequence induction and intubation may also be allowed if clinically indicated for the safety of the patient as determined by the attending anesthesiologist. Anesthesia will be maintained with isoflurane in fresh gas such as oxygen and/or air. No vasopressors will be administered at induction or during intubation unless the SBP is less than 80% of baseline for greater than 4 consecutive minutes. In that case, a rescue vasopressor such as phenylephrine will be given.

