We will record the infusion rate of Ang II, anesthetic level (i.e. end tidal agent concentration), HR, SBP, diastolic blood pressure, mean arterial pressure, and SpO₂ every minute for the duration of the study period if an infusion was initiated. Once the SBP is within 5% of baseline or greater, the infusion will be continued at that rate for 5 minutes. If the measured SBP significantly exceeds the baseline SBP by $\geq 15\%$, the infusion will be reduced or halted at the discretion of the team taking care of the patient. After 5 minutes of reaching the target pressure of within 5% of baseline or greater the final infusion rate will be recorded. At this time the third and fourth blood samples (10cc LC/MS blood sample, along with a 10 cc RIA blood sample) will be taken to measure the serum levels of different RAAS components associated with normalization of the SBP under general anesthesia. The infusion of Ang II will be discontinued. This will mark the end of the dose finding trial for the patient. Further vasopressor administration will be at the discretion of the team taking care of the patient but will not include Ang II. A fifth and final 10cc blood sample for LC/MS RAAS testing will be drawn 30 minutes after incision.

If the SBP for any enrolled patient does not drop below 80% of baseline in the first 10 minutes after intubation, Ang II will not be administered. However, we will still perform LC/MS RAAS 10 minutes after intubation, and LC/MS RAAS sampling 30 minutes after surgical incision for up to 15 previously enrolled patients as a comparison group (Arm 4). Once Arm 4 reaches 15 patients, any subsequent patients that do not experience a drop in SBP < 80% baseline will be excluded from the study and their LC/MS blood samples that were previously drawn will be discarded. However, we intend to analyze the RIA blood samples for up to 90 patients and these samples will not be discarded.

Subjects selection criteria

The study will recruit adult general surgery patients with underlying essential hypertension undergoing general anesthesia for elective general surgery. Patients will be recruited dependent upon their antihypertensive medication into the following arms.

Arm 1: Patients must be on ACE inhibitors, in addition they can also be on other classes of antihypertensive medication except for ARB.

Arm 2: Patients must be on ARBs, in addition they can also be on other classes of antihypertensive medication except for ACEi.

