Arm 3: Patients on any other antihypertensive medication, and must not be on an ACEi or ARB.

Arm 4: Patients who qualify for arm 1, 2, or 3 but whose SBP does not drop below 80% of baseline in the first 10 minutes after intubation.

- **Inclusion Criteria**

- Diagnosis of hypertension and treatment for greater than 2 months and on the following medications
 - ACE inhibitors, in addition they can also be on other classes of antihypertensive medication except for ARB
 - ARBs, in addition they can also be on other classes of antihypertensive medication except for ACEi
 - Any other antihypertensive medication, and must not be on an ACEi or ARB
- Patients undergoing general anesthesia
- American Society of Anesthesiologists physical status 1-3
- Age ≥ 40 given that hypertension is not prevalent below this age

- **Exclusion Criteria**

- American Society of Anesthesiologists physical status 4-6
- BMI > 40
- History of deep venous thrombosis / thromboembolic disease
- History of stroke,
- Baseline SBP of ≥ 160 mmHg,
- History of myocardial infarction or cardiac stents
- Difficult airway
- Asthma
- Diagnosis of congestive heart failure of any stage, regardless of preserved or reduced ejection fraction; this includes both systolic heart failure and diastolic heart failure;
- Diagnosis of chronic obstructive pulmonary disease of any stage; this includes diagnoses of chronic bronchitis and emphysema
- Pregnant patients (safety of Ang II in pregnancy is unknown)

- Patients at increased risk for venous thromboembolic events such as current diagnosis of cancer and/or diagnosis of blood clotting disorders
- **Sample Size**
Our goal would be to enroll and obtain data on 15 patients for each group: ACE group, ARB group, and patients on any other class of antihypertensive agent for greater than 2 months. In addition, we would like to obtain data for up to 15 patients in the comparison group (Arm 4). The sample size was chosen due to its similarity to the ATHOS II dose-finding trial.⁹ It would be our intent to continue enrolling patients until a sample size of 15 patients for all 3 experimental groups has been reached. Based on an estimated incidence of hypotension of 40-60%, we expect to have to consent approximately 90 patients.¹ This is not a multisite study.

Interventions and Interactions

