The primary outcome will be the mean dose required to increase the SBP in these 3 cohorts with essential hypertension (ACE inhibitor, ARB, or those on another class of hypertensive agents) to within 5% of baseline or higher. 15 patients will be selected to follow suit with other similar dose finding trials with vasopressors.¹⁰ The mean dose required to elevate SBP from the nadir to within 5% of baseline for each group will be compared for significance using a student's t-test and Bonferoni correction for multiple comparisons to determine if different doses of angiotensin 2 are required in patients chronically on ACE or ARB inhibitors. The dose-response data will be analyzed with linear regression to construct a dose response curve relating dose and percent increase in SBP from the nadir in the setting of general anesthesia. We will perform descriptive statistics on the patient population. Secondary outcomes will be the mean value for different components of the RAAS system in all 4 populations at different times prior to and during the surgical epoch;

Human Subjects Protection

Subject Recruitment Methods

Patients will be identified for participation in the Preoperative Assessment Clinic (PAC) prior to the day of surgery. Patients will be recruited by investigators and/or the study coordinator with the participation and collaboration of PAC attending and other staff present in the clinic involved in this study. We will attempt to recruit qualified subjects in a non-biased manner. Privacy will be protected because subjects will be recruited in the process of a confidential preoperative evaluation in the PAC. If they choose not participate no research record will be created other than to indicate that they declined to participate and as such there will be no contact information to destroy.

Informed Consent

Signed informed consent will be obtained from each subject. Research study members involved in the study will obtain informed consent. A copy of the signed consent will be given to the subject.

Confidentiality and Privacy

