Appendix 1: Data Collection Form

Study ID: _____

**A dose finding trial for angiotensin II (Giapreza) in hypertensive adults on
angiotensin converting enzyme inhibitors and angiotensin receptor blockers
with anesthesia-mediated hypotension**

DATA COLLECTION SHEET

A dose finding trial for angiotensin II (Giapreza) in hypertensive adults on angiotensin converting enzyme inhibitors and angiotensin receptor blockers with anesthesia-mediated hypotension

Study ID: _____ Age: _____ ASA PS: _____

Gender: M / F UPT: + / - / NA

Surgery date: _____ Surgical procedure: _____

Attending Anesthesiologist: _____

Antihypertensive group: ACE / ARB / other

Antihypertensive medication: _____ Duration of therapy: _____

Preoperative creatinine: _____ Diabetes: No / NIDDM / IDDM

Peripheral vascular disease: Y / N

DVT prophylaxis: SCD / SQ heparin / SQ enoxaparin / other _____

STUDY ID: _____

A dose finding trial for angiotensin II (Glipreza) in hypertensive adults on angiotensin converting enzyme inhibitors and angiotensin receptor blockers with anesthesia-mediated hypotension

1) Holding room data (Time: _____)

Vital signs	HR	
	NIBP/MAP	
	SpO ₂	

Medications taken DOS

LC/MS RAAS sample in holding
 WFBH labs—blood AND urine
 Urine NOT collected (reason): _____

2) OR pre-induction/Baseline (Time: _____)

NIBP/MAP	
----------	--

Induction

Time: _____

(1.5 mg/kg propofol, 0.8 mg/kg rocuronium; avoid pressors)

3) OR post-intubation

Time post-intubation	NIBP/MAP	Confirmatory BP (If <80% baseline)
1 min		
2 min		
3 min		
4 min		
5 min		
6 min		
7 min		
8 min		
9 min		
10 min		

IF ATII infusion started, see next page

IV fluid total PRIOR to ATII administration: _____

Time angiotensin II infusion started: _____

Goal BP +/- 5% of baseline, time reached: _____

ATII infusion at goal BP for 5 minutes, then:

VS/data	HR	
	NIBP/MAP	
	SpO ₂	
	ET Isoflurane (%)	
	Final angiotensin II rate (ng/kg/min)	

LC/MS RAAS sample

LC/MS RAAS sample 30 minutes post-incision

Time infusion stopped: _____

IVF total AFTER ATII administration complete: _____

If no hypotension (< 80% baseline) encountered:

Move to group IV (first 15 patients only)
 LC/MS RAAS draw 10 minutes post-intubation
 LC/MS RAAS sample 30 minutes post-incision
 >>OR<<
 Exclude patient from LC/MS analysis
 Discard first LC/MS sample from holding area

STUDY ID: _____

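### Arms 1-3 are defined by existing treatment, yet required dose is compared only by unadjusted t-tests, so a systematic case-mix difference could be read as a drug-class difference

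*Combined protocol and SAP*

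**What the plan says.** Under Subjects selection criteria, "Patients will be recruited dependent upon their antihypertensive medication into the following arms". Arm 1 is patients on an ACE inhibitor and Arm 2 is patients on an ARB, each with other classes allowed on top. Arm 3 is patients on "any other antihypertensive medication, and must not be on an ACEi or ARB". No randomisation, matching or stratification is described.

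In the Analytical Plan, "The primary outcome will be the mean dose required to increase the SBP in these 3 cohorts with essential hypertension". The group means "will be compared for significance using a student's t-test and Bonferoni correction for multiple comparisons", and the stated purpose is "to determine if different doses of angiotensin 2 are required in patients chronically on ACE or ARB inhibitors". The only regression is a different analysis: "The dose-response data will be analyzed with linear regression to construct a dose response curve". No arm term or patient characteristic is named for it. Patient characteristics are otherwise only to be described.

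The data collection form (Appendix 1) records age, ASA status, preoperative creatinine, peripheral vascular disease, duration of therapy and "Diabetes: No / NIDDM / IDDM". It also records the operating-room pressure taken before induction, of which the Design section says "This reading will be used as the baseline systolic blood pressure (SBP"). None of these enters the comparison of dose.

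**The concern.** Prescribers choose drug class for reasons that may also bear on how much vasopressor a patient needs. Arms 1 and 2 may carry additional antihypertensives, and day-of-surgery dosing follows clinic practice rather than the study. The arms may therefore differ systematically in ways that predict dose.

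An unadjusted t-test cannot separate such a difference from one linked to drug class. The reader is primed to credit drug class: the Background asks whether these patients respond differently, and the Design section expects ACE inhibitor patients to be more sensitive to Ang II and ARB patients less so. At stake is whether the trial reports that one class needs a different dose when the gap comes partly or wholly from case mix.

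**Working it through.** **Inputs from the documents.** 15 patients in each of Arms 1-3 (Design; Sample Size); Student's t-test with Bonferroni correction (Analytical Plan). The 15 per arm rests on precedent, with no effect size, SD or power, so it cannot be reproduced as a calculation. The one figure that can be reproduced is the roughly 90 patients to consent: 45 / 0.50 = 90 at the midpoint of the stated 40-60% incidence of hypotension (45 / 0.40 = 113; 45 / 0.60 = 75).

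**Assumptions.** Two-sided 0.05 over three pairwise tests, so 0.05 / 3 = 0.0167 each. Covariate-dose correlation within arms *r* = 0.3 to 0.5, and a systematic covariate shift *m* = 0.5 or 0.8 SD between two arms. None of these is given in the documents.

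**Step 1: bias.** With no true class effect, the expected difference in mean dose is *r* × *m*, in SDs of dose. The rejection rate is that of a noncentral t with 28 df and noncentrality *rm* / √(2/15), where √(2/15) = 0.365.

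| *m* | *r* | Bias (SD) | Noncentrality | False-positive rate for that pair |
|---|---|---|---|---|
| 0 | any | 0 | 0 | 1.67% |
| 0.5 | 0.3 | 0.15 | 0.41 | 2.5% |
| 0.5 | 0.5 | 0.25 | 0.68 | 4.2% |
| 0.8 | 0.3 | 0.24 | 0.66 | 4.0% |
| 0.8 | 0.5 | 0.40 | 1.10 | 8.8% |

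A larger trial does not cure this. The same 0.40 SD bias at 50 per arm gives 33.6%.

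**Step 2: familywise rate, and the effect of adjustment.** This was simulated with 20,000 trials per setting, the third arm lying midway. With 0.8 SD between the extreme arms and *r* = 0.3 / 0.5, the unadjusted tests reject at least once in 7.1% / 12.8% of trials. A linear model containing the covariate rejects in 4.4% / 4.2%. With no shift, both methods give 4.2-4.4%.

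**Step 3: chance imbalance.** With 15 per arm, at least one pair differs by more than 0.5 SD on a given covariate in about 36% of trials, even with no systematic shift. Averaged over all such trials, however, the t-test keeps its level: 400,000 simulated trials at *r* = 0.5 gave 1.65% per comparison.

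**Step 4: precision.** The unadjusted difference detectable with 80% power is 1.25 SD. Adjustment multiplies it by about √[(1 − *r*²) × VIF], where VIF (variance inflation factor) reflects covariate imbalance between arms.

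- Balanced (VIF = 1): 1.25 × √0.91 = 1.19 SD at *r* = 0.3, and 1.25 × √0.75 = 1.08 SD at *r* = 0.5.
- One covariate with an observed gap of 0.8 SD: VIF = 1 + 0.8² / (42 × 2/15) = 1.11. At *r* = 0.3, 1.25 × √(0.91 × 1.11) is about 1.26 SD, which is no gain.
- Three covariates explaining 10% of the variance, VIF = 1.25: 1.33 SD, a slight loss.

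**The case against.** **The comparison may be descriptive.** The primary outcome is the mean dose in each cohort of a small dose-finding study, and the plan nowhere says that class causes a difference. For the question of what dose patients on each class need, with their usual case mix, unadjusted means are the right summary. This stands, and is why those means should stay in the report. It does not cover a significance test meant to decide whether chronic ACE inhibitor or ARB users need a different dose, which will be read as being about the drug.

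**Chance imbalance is not confounding.** A reader might infer from the 36% figure in Step 3 that small arms inflate the error rate. They do not, because the nominal rate already allows for chance gaps. The argument rests wholly on systematic differences, which non-random allocation makes plausible but which the documents do not quantify.

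**Baseline SBP is not a clean covariate.** It is tempting to treat it as a safe pre-treatment value, especially as the target is a percentage of it. It precedes Ang II, but it is read just before induction in patients treated for more than two months. It follows the exposure being compared, and drug class may affect it. Adjusting for it could remove part of the difference of interest. The pressure that triggers the infusion is more exposed still, since the fall may lie on the path from drug class to dose. Age is clearly free of this objection.

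**Conclusion.** The point holds as a risk of confounding in the arm comparison. The plan has no safeguard against it, although usable data are already collected. Under the assumed range, the per-comparison false-positive rate rises from 1.67% to about 2.5-4.2% for a systematic 0.5 SD shift and to about 4.0-8.8% for 0.8 SD; adjusting for the covariate responsible brings it back to nominal. These figures show what would follow if such a shift exists. The documents do not establish that it does.

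A reader might also infer that the unadjusted test necessarily wastes precision. That is not supported: the gain depends on covariate strength and balance, neither of which is known, and can be nil or slightly negative. Nor can adjustment turn this into a causal comparison, since unmeasured confounding remains. The case for the change is modest, but the change is nearly free.

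**What to change.** In the Analytical Plan, prespecify the following:

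- **Main comparison:** one linear model of required dose (log scale if skewed) on arm and age, from which the three Bonferroni-corrected pairwise contrasts and their confidence intervals are taken.
- **Alongside it:** the unadjusted means and t-tests, as the description of each cohort.
- **Named sensitivity model:** add baseline SBP, noting that it is measured on chronic therapy and may be affected by drug class.
- **Exploratory only:** any model containing the SBP that triggered the infusion, because the fall in pressure may be a mediator.
- **Interpretation:** arm differences are described as associations with drug class.

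The cost is a few sentences and no new data. Age uses one of the 45 − 3 = 42 residual degrees of freedom, and baseline SBP uses a second in the sensitivity model. Intervals may widen slightly if the covariates prove weak and imbalanced. Naming the covariates in advance also prevents their being chosen after the doses are seen.

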Following intubation and before initial surgical incision, the BP will be checked using a non-invasive BP cuff every minute for 10 minutes. If a SBP that is less than 80% of the baseline reading is detected, the clinical team will immediately cycle the BP cuff in order to confirm the presence of hypotension. At this point an infusion of Ang II will be initiated at 2 ng/kg/min through a peripheral IV (although the recommended starting dose of Ang II is listed as 20ng/kg/min, this dosing regimen is based on patients in shock. The package insert also states that doses as low as 1.25ng/kg/min may be effective). Starting at a low dose will be important since patients taking ACE inhibitors may be more sensitive to Ang II. The BP will be checked every minute. The half-life of angiotensin 2 is < 1 minute and time to peak pharmacologic affect is less than 30-35 seconds so it will be necessary to monitor the blood pressure once per minute. The infusion will be increased at the discretion of the clinical team based on the response of the patient until a SBP within 5% of the baseline SBP has been achieved (although the rate will not be increased by more than 15ng/kg/min at a time and the rate will not exceed 80ng/kg/min based on the package insert dosing instructions). If the patient remains hypotensive despite use of the maximum dose of angiotensin II, then angiotensin II will be discontinued, the patient will be excluded from the study, and the blood pressure will be treated using conventional vasopressors. If a patient experiences SBP < 80% baseline for greater than four consecutive minutes after initiating Ang II, then a rescue vasopressor such as phenylephrine will be administered. This will be important for patients taking ARBs as they may be less sensitive to Ang II.

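### The dose-response regression names no unit of analysis and makes no allowance for titrated, repeated readings, so its slope can be biased for the effect of raising the rate in a patient

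*Combined protocol and SAP*

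**What the plan says.** The Analytical Plan gives the dose-response analysis one sentence: "The dose-response data will be analyzed with linear regression to construct a dose response curve relating dose and percent increase in SBP", measured from the nadir under general anesthesia. No unit of analysis, arm term or correlation structure follows, here or elsewhere in the combined protocol and SAP.

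The Design section describes how the data arise:

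- **Dose.** Every patient starts at 2 ng/kg/min. Then "The infusion will be increased at the discretion of the clinical team based on the response of the patient", with limits on step and ceiling: "although the rate will not be increased by more than 15ng/kg/min at a time and the rate will not exceed 80ng/kg/min". The rate that first brings SBP to target is held for 5 minutes.
- **Readings.** "We will record the infusion rate of Ang II, anesthetic level (i.e. end tidal agent concentration), HR, SBP" and other vital signs each minute of an infusion. The form in Appendix 1 also has one line for the final rate. The plan therefore yields two data sets: about one reading per minute, and one final rate per patient.
- **Rescue.** After more than four consecutive minutes below 80% of baseline, "then a rescue vasopressor such as phenylephrine will be administered".
- **Patients still hypotensive at the ceiling.** For them, "angiotensin II will be discontinued, the patient will be excluded from the study".
- **Expected sensitivity.** The section states that "patients taking ACE inhibitors may be more sensitive to Ang II" and refers to "patients taking ARBs as they may be less sensitive to Ang II".

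**The concern.** Dose is an outcome of the patient's response, not an assigned factor. A patient reaches a high rate by being resistant or by starting from a deep nadir. Across patients, resistance flattens a fitted line and a deep nadir can steepen it. An ordinary fit mixes both with the drug effect. Pooling minute readings also treats many readings from one patient as independent.

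This is the plan's only analysis of how SBP changes with dose. A reader would naturally take its slope as the rise to expect from increasing the rate in a patient. Two analysts could follow the sentence faithfully, one on minute readings and one on final rates, and report quite different slopes.

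**Working it through.** The plan states no figure for this analysis, so there is none to reproduce. The check is exact arithmetic followed by simulation.

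**Arithmetic.** The rise needed to reach 95% of baseline is 95/nadir − 1, with the nadir as a percent of baseline.

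- Nadir 79%: 95/79 − 1 = 20%. Nadir 60%: 95/60 − 1 = 58%.
- *Resistance flattens.* Take two patients with nadir 70%, so both need 95/70 − 1 = 35.7%. Assume slopes of 1.5 and 1/1.5 = 0.67 percent per ng/kg/min. Their final rates are 35.7/1.5 = 23.8 and 35.7 × 1.5 = 53.6 ng/kg/min. The rise is the same at both rates, so the final-rate slope is 0 although both patients respond.
- *Nadir depth steepens.* Take two patients who each gain 1 point of baseline per ng/kg/min, with nadirs of 79% and 60%. They need 16 and 35 ng/kg/min. The final-rate slope is (58.3 − 20.3)/(35 − 16) = 2.00 percent per ng/kg/min. Their own slopes are 100/79 = 1.27 and 100/60 = 1.67, mean 1.47.

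**Simulation inputs from the documents:** 3 × 15 = 45 infused patients, start 2, cap 80, steps of at most 15 ng/kg/min, minute readings, 5-minute hold, 20-minute limit (Interventions and Interactions).

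**Assumed inputs, not in the documents:** nadir 60-79% of baseline, median effect 1 point per ng/kg/min, reading noise 3 points, equal steps of 5-15, response linear either in points of baseline or in percent of nadir. Sensitivity is log-normal; a log SD of 0.2 or 0.4 puts one SD at a factor of e^0.2 = 1.22 or e^0.4 = 1.49.

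Ordinary regression slope, as percent of the true mean patient slope (range over steps and both scales):

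| Log SD | Pooled minutes, no drift | Final rates, no drift | Pooled, SBP drifting up 0.5 points/min | Final rates, same drift |
|---|---|---|---|---|
| 0 | 100-109 | 99-130 | – | – |
| 0.1 | 95-105 | 89-112 | 101-119 | 94-127 |
| 0.2 | 83-94 | 65-76 | 89-108 | 72-94 |
| 0.4 | 52-70 | 25-34 | 59-78 | 32-43 |
| 0.8 | 18-25 | −4 to 18 | 21-33 | 4-18 |

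- **Class difference only** (assumed ACE ×1.5, ARB ÷1.5, one curve for all): 65-75 pooled, 36-40 final.
- **Rescue-affected readings left in** (step 3, about 12-14 of 45 rescued): pooled 101-107 at log SD 0.2 and 78-79 at 0.4.
- **Other assumptions.** A second simulation (step 5, nadir 62-79%) gave 0.76 pooled and 0.45 final against a true 1.01 at a coefficient of variation of 0.3. At 0.5 it gave 0.62 and 0.23 against 1.06. The final-rate figures depend more on the assumptions than the pooled ones.
- **Standard error.** The ordinary pooled standard error was too small by a factor of 1.3-2.0 at log SD 0.1 and 1.8-2.8 at 0.2-0.8.

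**Candidate repairs.** The mean of within-patient slopes was 1.02 against 1.01, and 1.07 against 1.06, in the second simulation. The choice of time term matters:

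| Condition | Mixed model without time | Mixed model with linear time |
|---|---|---|
| Linear drift of 0.5 points/min, no lag | 103-118% | 98-104% |
| Response half-life 0.5 min, no drift | 97-104% | about 90-94% |
| Response half-life 1 min, no drift | 97-104% | about 65-70% |

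The Design section puts the drug's half-life below 1 minute, so the last row is an upper bound if the response follows the drug. During the hold the dose is constant while SBP may still be catching up, and a time term absorbs that drug effect.

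**The case against.** **The wording does not exclude per-arm or per-patient fits.** True, and per-arm fits would remove the bias that comes from class differences alone. They are not planned, however, and they leave variation within an arm.

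**The bias is not inevitable.** This stands. A reader might infer that an ordinary fit always misses the within-patient effect, or always flattens it. The documents support neither. With equal or nearly equal sensitivity the pooled fit is close to the truth or above it. Drift or retained rescue readings can push it upward. The protocol says only that the drug classes may differ.

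**The plan promises a curve, not a within-patient effect, standard error or interval.** Also true. The standard-error point therefore applies only if precision is reported. But a curve in a dose-finding trial will be read as what a change of rate does, and the plan should say whether it may be.

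**A richer model brings its own bias.** This stands for a time-adjusted model. A reader might infer that time belongs in the main model because dose and time rise together. The lag results show that this could do more harm than the drift it removes, and the documents do not say which problem is larger.

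**Conclusion.** The point holds in a limited form. The analysis is under-specified for response-titrated, repeated data. A pooled or final-rate fit can be biased for the effect of raising the rate in a patient: usually flattened once sensitivity varies moderately or more, and little biased or biased upward at small spread or with spontaneous recovery. Pooled minutes would also overstate precision.

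The sizes rest wholly on assumed sensitivity spread, nadir distribution, noise, step and drift, for which the documents give no values. They show what is possible and do not predict this trial's result.

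A reader might also infer that the dose-finding result is undermined. It is not: the primary comparison of mean required dose does not use this regression, and the curve is not listed as a primary or secondary outcome. This is an improvement to consider.

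**What to change.** Replace the sentence in the Analytical Plan with wording such as:

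> Dose-response data are the per-minute readings during Ang II infusion. Percent SBP change from nadir will be analysed with a linear mixed model with dose, arm and arm-by-dose as fixed effects and a random intercept and random dose slope per patient. The slope and 95% CI will be reported for each arm. If the model does not converge, per-patient slopes will be summarised by arm. Readings after any rescue vasopressor will be censored and earlier ones kept. Models adding time since start of infusion and concurrent end-tidal agent are sensitivity analyses. The numbers of patients and readings affected by rescue, and of patients withdrawn at the maximum rate, will be reported.

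Add as limitations that dose and time rise together within a patient. Without a time term, spontaneous recovery inflates the slope, by up to about 20% at an assumed drift of 0.5 points/min. With a linear time term, a lagged response deflates it, to about 65-70% of the truth at a 1-minute half-life without drift.

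Any use of readings from patients withdrawn at the maximum rate must be reconciled with the Design statement that they are excluded from the study. In simulation, keeping or dropping them moved the slope by at most about 1.5 percentage points.

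The cost is small: some extra analysis work and wider, more honest intervals than a pooled fit would give. Rate, SBP and end-tidal agent are already recorded each minute. A field for the time of rescue may be needed on the form. A patient who reaches target at the starting rate has no slope of his or her own, so the fallback should report how many such patients there are.
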